9.5 Overdose

Inadvertent overdosing, such as administration of a higher dose than dictated in the protocol, should be followed by rigorous monitoring for potential adverse reactions. Patients experiencing toxicities upon misdosing or overdosing must be treated at the discretion of the treating physician with adequate supportive care and followed until recovery.

All cases of misuse of enobosarm, including overdose, should be reported to the EMERALD Trial Coordinator.

10 STATISTICAL CONSIDERATIONS

10.1 Method of Randomisation

The sequence of allocations will be centrally generated by the LCTC study statistician using the Stata package *ralloc* employing permuted block randomisation with variable block length, and 3:1 (enobosarm : control) allocation to the two treatment arms.

10.2 Outcome Measures

10.2.1 Primary outcome measures

Change in the proliferation marker Ki67 (% positive tumour cells) determined by tissue immunohistochemistry at baseline and 2 weeks.

10.2.2 Secondary outcome measures

- Amount of cleaved caspase 3 determined by tissue immunohistochemistry at baseline and two weeks
- Expression of PSA, Gross Cystic Disease Fluid Proteins (GCDFP)-24 & -15; PgR, GREB1 by tissue immunohistochemistry at baseline and two weeks
- Amount in serum levels of circulating steroidogenic hormones oestradiol, oestrone, oestrone sulfate, androstenedione, follicle stimulating hormone, luteinizing hormone, DHT, progesterone, sex hormone binding globulin (SHBG) and total testosterone in blood determined by blood assay at baseline and two weeks; free testosterone to be derived from SHBG and total testosterone
- Amount in serum levels of PSA and steroidogenic hormones determined by blood assay at baseline and two weeks

10.2.3 Safety Endpoints

- Occurrence of grade 3+ toxicity as classified by NCI-CTCAE v 4.03
- Occurrence of serious adverse events
- Withdrawal from trial treatment due to toxicity
- Experience of delay to scheduled surgery/neoadjuvant chemotherapy or endocrine therapy

10.3 Sample Size

In the absence of a clearly defined or a clinically relevant difference for Ki67, the primary efficacy parameter will be the probability that the response in one group will be “better” than the response in the other group. This may be referred to as the Probability of Benefit or PoB, and is directly estimated by the (scaled) Mann-Whitney statistic; in the present context a “good” response is a greater reduction in the Ki67 index in the treated arm, and a useful reduction in Ki67 is taken to be a PoB of 0.67 (odds of 2:1 favouring the intervention, and equivalent to a standardised effect size of 0.62).

To demonstrate a PoB (in terms of a reduced Ki67 index) of 0.67, with 5% two-sided significance and 90% power we require 147 patients (with allocation 3:1 enobosarm: “treatment as usual” control). This can be achieved from a minimum of 7 sites assuming an average of 2 pts/site/month and 2 sites opened/month (actually yielding 150 patients), with duration of accrual of 14 months.

The recruitment rate/site estimate is based on the recruitment to the POETIC study (Smith et al. 2011) from the selected centres. Based on previous studies loss to follow-up is expected to be minimal (<1%) as this is a highly motivated group of participants, follow-up is brief and assessment non-invasive.

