7.3.6 Surgery/Research Core Biopsy

Surgery

The breast surgery will be pre-arranged before the patient begins the enobosarm treatment as part of the patient's standard of care. This visit should be within 24 hours of taking the last dose of enobosarm, this may be the day before surgery or the day of surgery depending on the time the last dose was taken and the time of surgery. Samples taken at surgery should ideally be taken via core biopsy (2 cores) once the tumour has been removed BUT BEFORE the tissue has been placed in formalin.

Research Core Biopsy

Patients who have pre-arranged neoadjuvant chemotherapy or endocrine therapy in place of surgery or before surgery will be required to have an additional core biopsy using a core-cut or tru-cut device under imaging guidance prior to commencement of neoadjuvant chemotherapy/endocrine therapy. All efforts should be made to coincide this biopsy with any planned interventions such as insertion of marker clips (for example to mark tumour site in case of complete pathological response to neoadjuvant chemotherapy). Two cores should be taken (one for an FFPE block and one for the AllProtect sample (see Section 8)). If only one core is available due to the size of the tumour or the patient does not wish to have multiple cores (due to pain at the time of the procedure), the core MUST be used for the FFPE block.

The following samples will be collected for all patients at Visit 2:

- Blood samples
- Core taken and placed in formalin to create an FFPE block (from excised tumour or via research core biopsy)
- Core taken and placed in AllProtect solution (from excised breast tumour tissue or via research core biopsy)

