10.5.8 Analysis of primary and secondary outcomes

The primary analysis will be a Mann-Whitney test comparing the change in Ki67 index from baseline between the two arms. The null hypothesis is that enobosarm is no more effective than standard care alone in terms of reduction in Ki67 score from baseline; that is, the Probability of Benefit is not statistically different from 0.5, while the alternate hypothesis is that addition of enobosarm is superior to standard care alone with a Probability of Benefit of

0.67 or more. Results will be presented in terms of the mean, median and SD of the baseline and final Ki67 scores by arm together with the Mann-Whitney statistic and p-value.

Sensitivity analyses

A sensitivity analysis will be performed with an analysis stratified on baseline Ki67. Similar analyses will be performed on secondary efficacy endpoints.

Tests of assumptions

Like the t-test, the Mann-Whitney test may fail to detect a shift in location if there is also a change in variance, hence as a test of shift in location it assumes equal variance. If the primary analysis or the stratified analysis fails to demonstrate statistical significance then a Beta Regression Model will be fitted that simultaneously estimates changes in mean and location, including terms for baseline and treatment for both mean and scale parameters. If the Beta regression model gives a p value < 0.05 for the treatment effect on the mean then the result will still be declared statistically significant.

For secondary endpoints comparison of change from baseline will be performed by a suitable regression-type model including terms to adjust for baseline and account for differences in variance.

Subgroup analyses

No subgroup analyses are planned.

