12 ETHICAL CONSIDERATIONS

12.1 Ethical Considerations

The trial will be conducted to conform to the principles of the Declaration of Helsinki as adopted by the 18th World Medical Assembly, 1964, and amendments.

The study will be conducted in accordance with the EU Directive 2001/20/EC, the Medicines for Human Use (Clinical Trials) Regulations 2004 and the principles of Good Clinical Practice.

Patients will be asked to consent that data are recorded, collected, stored and processed and may be transferred to other countries, in accordance with any national legislation implementing the EU Data Protection Directive (95/46/EC).

This study may be terminated at the request of the CI, TSG, REC, IDSMC or the MHRA if, during the course of the study, concerns about the safety of further dosing emerge.

The CI will update the REC of any new information related to the study drug when appropriate and this will also be disseminated to the Principal Investigators at each trial centre.

- Enobosarm could theoretically stimulate proliferation in some tumours. This would be an important finding and once the subtype was formally identified would represent an exclusion from future enobosarm/SARM studies
- Patients may experience side effects as a result of enobosarm
- Patients, as a result of providing translational blood samples, may experience additional pain, bruising, infection or inflammation at the sample site, and/or feel faint during the blood collection procedure.
- Patients will have to make additional clinic visits whilst on the study treatment and if they require a research core biopsy (if this does not coincide with insertion of a marker clip)

12.2 Patients who will require a research core biopsy in order to join the study will be asked for specific consent on the informed consent form. The procedure and the additional risks will be described in the patient information sheet and it will be made clear the procedure is optional. Ethical Approval

The trial protocol has received the favourable opinion of the Haydock Research Ethics Committee which, in line with HRA Approval, has also been given on behalf of all research sites. A copy of all site approval documents and a copy of the PIS and ICF on local headed paper should be forwarded to LCTC before patients are entered. The REC Number for EMERALD is 16/NW/0807.

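### Section 10.3's 147 patients is a t-test size; the planned Mann-Whitney test has about 87 to 89% power there, with no allowance for non-evaluable Ki67 pairs

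*Protocol*

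**What the plan says.** Section 10.3 makes the PoB the primary efficacy parameter, to be estimated by the scaled Mann-Whitney statistic. It says that "a useful reduction in Ki67 is taken to be a PoB of 0.67", which it calls "equivalent to a standardised effect size of 0.62". It then says that "with 5% two-sided significance and 90% power we require 147 patients", "with allocation 3:1 enobosarm" to control. The test is fixed in 10.5.8: "The primary analysis will be a Mann-Whitney test comparing the change in Ki67 index from baseline between the two arms".

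On attrition, 10.3 says that "loss to follow-up is expected to be minimal (<1%) as this is a highly motivated group of participants, follow-up is brief and assessment non-invasive". Projected accrual is 150. Section 7.7 plans no replacement of patients lost to follow-up.

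The endpoint is a change in Ki67, so it needs a baseline and a final tumour sample. Baseline tissue is what remains of the diagnostic core (7.6.4, 8.2). The final sample is a core from the excised tumour or, for neoadjuvant patients, a separate procedure: they "will be required to have an additional core biopsy using a core-cut or tru-cut device under imaging guidance" (7.3.6). The sentence printed with the heading of 12.2 says of this research core that "it will be made clear the procedure is optional".

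**The concern.** A sample size justified through the PoB and the Mann-Whitney statistic should be a Mann-Whitney sample size. If the number comes from a t-test at the equivalent normal effect, the stated 90% belongs to a test that is not the primary one.

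The attrition sentence raises a second issue. Loss to follow-up and loss of an evaluable Ki67 pair are different things. A patient can attend every visit and still have too little diagnostic tissue left, or no usable final core. The full analysis set in 10.5.1 requires an assessed primary outcome, and 10.5.5 attempts imputation only when more than 10% of patients lack a Ki67 value. Missing pairs up to that level therefore come straight off the effective sample size.

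At stake is whether the power in the protocol is the power of the planned analysis on the patients who can be analysed.

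**Working it through.** **Inputs (10.3, 10.5.8).** PoB 0.67; two-sided 5%; 90% power; 3:1 allocation, so 110 enobosarm and 37 control at 147; Mann-Whitney primary test. The normal quantiles are 1.960 and 1.282. The product of the allocation fractions is 0.75 × 0.25 = 0.1875.

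**Effect conversion.** Under a normal shift, d = √2 × Φ⁻¹(0.67) = 0.622, which agrees with the protocol's 0.62.

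**Reproducing 147.** Two-sample t-test, noncentral t, 110 versus 37:

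- Power is 90.0% at d = 0.62 and 90.2% at d = 0.622.
- Solving for 90% power gives N = 147.7 at d = 0.62 and 146.7 at d = 0.622.

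So 147 is the t-test size.

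**Size for the Mann-Whitney test.**

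- Noether: N = (1.960 + 1.282)² / (12 × 0.1875 × 0.17²) = 10.507 / 0.065025 = 161.6, so 162.
- Normal-approximation size divided by the asymptotic efficiency 3/π: (1.960 + 1.282)² / (0.1875 × 0.622²) = 144.8, and 144.8 / 0.955 = 151.6. Dividing the t-test's 147 instead gives 153.9.
- Normal-shift asymptotics with separate null and alternative variances: 153.2 to 154.2.
- Simulation under a normal shift: power 89.4% at 153 and 89.9 to 90.4% at 156, so about 155 is needed.

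None of these Mann-Whitney calculations gives 147.

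**Mann-Whitney power at 147 evaluable, PoB 0.67.**

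- Simulation, normal shift: 88.5 to 88.8%.
- Normal-shift asymptotics: 88.6 to 88.9%.
- Noether: Φ(√(147 × 2.25) × 0.17 − 1.960) = Φ(1.132) = 87.1%.
- Other shapes at the same PoB: 88.7% for a logistic shift; 87.6% and 89.8% for two exponential alternatives.

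**Effect of non-evaluable pairs.** The protocol gives no tissue-failure rate. The 5% and 10% rows are illustrative assumptions; the 1% row applies the protocol's ceiling for loss to follow-up to Ki67 pairs.

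| Non-evaluable | Evaluable of 147 | Mann-Whitney, normal shift (simulation) | Noether |
|---|---|---|---|
| 0% | 147 | 88.5–88.8% | 87.1% |
| 1% | about 145 | 87.7–88.1% | 86.7% |
| 5% | about 139–140 | about 87% | about 85% |
| 10% | 132 | about 85% | 83.4% |

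Inflating even the stated 147 for a 1% loss would give 147 / 0.99 = 148.5, so 149. The 147 therefore contains no allowance at all.

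**The case against.** The strongest reply is that the discrepancy is trivial. Simulating the actual test gives about 88.6%, within 1.5 points of the claim. Noether's formula uses the null variance and is conservative here: it asks for 162 where simulation needs about 155. This stands. The test mismatch is an imprecision, and one plausible alternative reaches 89.8%.

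Second, 10.5.8 lets a Beta regression rescue a non-significant result, so the chance of declaring success is at least the Mann-Whitney figure. A rough proxy, significance on either a Mann-Whitney or a t-test, gives about 91% at 147. This stands only in part. Section 10.3 ties its 90% to the PoB and the Mann-Whitney statistic, not to that two-step rule, and a second chance at significance has its own type I error cost.

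Third, the design has safeguards. Projected accrual is 150, which is 3 / 147 = 2% above target. Baseline tissue already exists. Standard-care resection blocks are also requested (8.2). A single research core must go to the block used for the primary endpoint (7.3.6, 8.2). Only neoadjuvant patients need the extra biopsy, and their share is not stated. All of this makes heavy tissue loss less likely. It does not close the gap: with all 150 evaluable, Noether gives Φ(√(150 × 2.25) × 0.17 − 1.960) = 87.8%, and 150 is still below the roughly 155 needed under a normal shift.

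Fourth, 12.2 can be read as making the core a condition of joining, with specific consent, and optional only in the sense of voluntary. That reading is fair, so the conflict with 7.3.6 is one of wording, though the two passages still do not say the same thing.

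A reader might go further and infer that the figure below 1% is wrong. The documents do not show that. It is attributed to previous studies and concerns loss to follow-up; the point is only that it does not measure sample evaluability.

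**Conclusion.** The point holds in a limited form. The 147 is a t-test size. The planned Mann-Whitney test has about 88.5 to 89% power with 147 evaluable patients under a normal shift and 87% by Noether; 90% needs about 155 or 162. This part costs 1 to 3 points and rests only on the protocol's inputs and the assumed shape of the alternative.

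The missing allowance for non-evaluable pairs is a separate gap. Its size cannot be fixed from the documents: power is about 87% if 5% are lost and about 85% if 10% are lost (Noether about 85% and 83%), and both rates are assumptions. The 10% in 10.5.5 is a trigger for imputation, not an expected rate. What the text does contradict is its own description of assessment as non-invasive.

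Three stronger inferences are not supported. One is that the trial is seriously underpowered, or that 85% is its real power. Another is that the reference to 2:1 odds (PoB 0.6667, Noether 169) should replace the 0.67 that 10.3 specifies. The third is that a baseline-adjusted analysis would remove any need for more patients: that gain depends on the baseline-to-final Ki67 correlation, which the protocol does not give.

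**What to change.** Keep 147 and revise 10.3 as follows:

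- State that 147 evaluable patients give about 87 to 89% power for the Mann-Whitney test at PoB 0.67, and name the method (simulation under a normal shift, Noether, or both). If 90% is to be kept, about 155 evaluable patients are needed, or 162 by Noether.
- Remove the description of assessment as non-invasive.
- Keep the figure below 1%, for loss to follow-up only.
- Add a separate assumed fraction of non-evaluable Ki67 pairs with the resulting power, for example at 5% and 10%, labelled as illustrative.

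Reconcile the required research core in 7.3.6 with the optional one in 12.2, so that it is clear whether a neoadjuvant patient can be randomised and then have no final Ki67 sample.

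Keeping 147 costs only rewording, with no change to accrual or procedures. The price is a stated power slightly below 90%.

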10.4 Interim Monitoring and Analyses

There is no stopping rule for efficacy or futility because there is no formal clinical definition of success and the intervention is not intended as a formal practical treatment. Stopping early on safety grounds is possible however, and a single ISDMC (Independent Safety and Data Monitoring Committee) meeting to review safety will be convened when half of the target number of patients has been evaluated for outcome. The analysis conducted by the Trial Statistician will be unblinded. The results of any efficacy analysis will be confined to the ISDMC and Trial Statistician, and the results of the review will be regarded as guidance only.

10.5 Analysis Plan

Statistical analyses will be performed in Stata v13 or higher. The trigger for the statistical analysis is the end of the trial.

10.5.1 Patient Groups for Analysis

Full Analysis set: In order to follow the Intention to Treat (ITT) principle this will consist of all randomised patients with assessment of the primary outcome excepting for: a) patients withdrawing consent between randomisation and starting therapy b) patients withdrawn from the study after randomisation because of irregularities with the consent process and c) patients whose information determining ineligibility existed before randomisation but was not read until after randomisation. Mis-randomised patients will be analysed as randomised.

Per protocol (PP) set: This will consist of those patients in the Full Analysis set without any major protocol deviations.

Safety set: All patients.

Major deviations from protocol that lead to exclusion of a patient from the per-protocol set will be those that either prevent evaluation of the primary endpoint or which imply insufficient exposure to reasonably expect a treatment effect. While it is possible to identify some deviations that will be a priori catastrophic (e.g. missing primary endpoint or missing all the treatment doses) it is difficult to determine in advance the impact of many others: for instance

would missing $\frac{1}{2}$ of the dose for each day of treatment have the same impact as missing the dose completely on $\frac{1}{2}$ of the treatment days? And would the impact differ depending on whether the missed days were early or late in the treatment period? A table of foreseen major deviations together with provisional assessments of impact is provided below (Table 3), but the final decision will be made in a review towards the end of the study before data lock. Patients who are excluded because of missing baseline or response data may still be included in the ITT population if the missing values can be imputed (see section 10.5.5). Minor violations by definition do not matter in this sense and will be ignored.

Efficacy analyses will be performed on the full analysis set and the per protocol set. Safety summaries will be performed on the safety set.

Table 3 Foreseen Major Deviations

Foreseeable deviation	Action
Missing primary endpoint	Exclude from per protocol analysis
All treatment doses missed	Exclude from per protocol analysis
Samples outside allowable window	Review and assign overall severity (0-1) weight*
Assessments outside allowable window	Review and assign overall severity (0-1) weight*
Some treatment days missed	Review and assign overall severity (0-1) weight*
Inadequate doses taken	Review and assign overall severity (0-1) weight*
Multiple deviations	Review and assign overall severity (0-1) weight*
*Patients may be excluded from per protocol analysis if weight is >0.5, included otherwise	

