7 ASSESSMENTS AND PROCEDURES

7.1 Laboratory Screening Procedure

7.1.1 AnR Staining

AnR staining should be conducted on all biopsy samples of early breast cancer in females over 45 years of age at the same time as ER, PR and HER2 testing of the diagnostic sample.

Ethical approval has been granted to perform additional diagnostic testing on all patient samples who meet the following criteria:

- Female
- Over 45 years of age
- Invasive breast cancer

Each staining result should be recorded on the LCTC Portal pre-screening log along with:

- patient gender (female)
- date of birth
- ER, PR and HER2 status
- Grade and breast cancer histological subtype

Results for all AnR staining should be included alongside the ER, PR and HER2 results on any pathology reports for all patients, and for should be available for the next MDT.

Positive result

If a result comes back ER and AnR positive then please inform the research nurse working on the trial or the principal investigator as soon as possible.

Negative result

If the ER or AnR result is negative this patient should not be approached to join the study. Their result should be recorded on the pre-screening log and no further additional testing should be carried out on this sample for the purposes of this research.

Please follow SSEME_D036 EMERALD Pathology Manual for more information on the IHC staining process.

Antibodies will be provided for the AnR staining.

7.2 Schedule of Trial Procedures – Table 2

Time Points	Screening	Screening	Baseline (Visit 1)	Mid-Treatment Phone Call	Tissue Collection (Visit 2)	End of study/ Follow up (Visit 3)	Premature Discontinuation
Day Assessments	-28 days	-14 days	Day 0	Day 7	Day 14 (+4 days)	Day 21 - 28 (+4 days)	
Informed Consent		X					
Eligibility Checklist		X					
Demography		X					
Medical History		X					
Breast ultrasound, mammogram and/or MRI	X						
Tumour size measurement (radiological)	X						
Physical examination including vital signs		X					
Symptom led physical examination					X	X	X
Height			X				
Weight			X		X	X	X
ECG		X ¹			X ¹		
ECOG Performance Status		X	X		X	X	X
Haematology and clinical biochemistry ²		X	X		X	X ³	X
Tissue analysis for AnR expression (on diagnostic tissue) ⁴	X				X ⁵		
Excised tumour tissue biopsy or research core biopsy					X ⁶		
Dispense study drug			X				
Study drug compliance				X	X		
Adverse events			X	X	X	X	X
Concomitant medication			X	X	X	X	X
Collection of blood – trial sample			X		X ⁷		X

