10.5.5 Missing data

No adjustment for missing data will be made for secondary endpoints. If more than 10% of patients have missing baseline or final Ki67 values, then multiple imputation will be attempted for these variables, performing at least 10 separate sets of multiple imputations by treatment arm using chained equations, as implemented in Stata v13 or later. Examples of variables to be included in the imputation process will be baseline and final values of other response variables, and covariates predictive of survival such as age and performance status.

The multiply-imputed data sets can then be recombined for formal analysis, either using the *mim* command prefix or if necessary a bespoke routine to estimate parameter values and combine them using Rubin's rules.

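### Serum hormone and PSA endpoints are analysed only in patients with an assessed Ki67, so up to 14 of 147 patients with usable blood could be left out for an unrelated reason

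*Protocol*

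**What the plan says.** Section 10.5.1 of the protocol defines the full analysis set: "this will consist of all randomised patients with assessment of the primary outcome excepting for" three groups, a) to c). These are withdrawal of consent before starting therapy, consent irregularities, and ineligibility information that existed before randomisation but was read only afterwards. Of the per-protocol set it says: "This will consist of those patients in the Full Analysis set without any major protocol deviations". It then fixes where efficacy is analysed: "Efficacy analyses will be performed on the full analysis set and the per protocol set". No other efficacy set is defined.

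Section 10.2.1 makes change in Ki67 the primary outcome. Section 10.2.2 lists the secondary outcomes, among them "Amount in serum levels of PSA and steroidogenic hormones determined by blood assay at baseline and two weeks". Section 10.5.8 calls the secondary endpoints efficacy endpoints, so the rule on sets covers them.

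Two provisions qualify this. Section 10.5.1 allows patients excluded for missing baseline or response data back into an ITT population if the values can be imputed. Section 10.5.5 attempts imputation of Ki67 only when more than 10% of patients lack a baseline or final value. For the other endpoints it says: "No adjustment for missing data will be made for secondary endpoints".

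**The concern.** Ki67 needs two evaluable tissue samples; the serum endpoints need two blood samples. Tying the serum analyses to Ki67 removes valid randomised data for a reason that has nothing to do with hormones or PSA. It also makes membership of the serum analyses depend on how many Ki67 readings fail across the whole trial: with 14 failures those patients are out, and with 15 they may come back.

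Two things are at stake. One is precision on twelve endpoints. The other is that the serum comparison becomes a comparison of patients with evaluable tissue. If tissue were missing more often after stopping drug, that selection would fall on one arm, because controls receive neither drug nor placebo (section 9.1).

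The primary Ki67 comparison and the safety summaries are not affected.

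**Working it through.** **1. Plan's own figure.** Section 10.3 gives N = 147 for a standardised effect of 0.62 (probability of benefit 0.67), two-sided 5%, 90% power, 3:1 allocation. By the normal approximation, control patients = (1 + 1/3) × ((1.960 + 1.282)/0.62)² = 36.4. That is 145.8 in total before rounding, or 37 controls and 148 in total after. A noncentral-t calculation with effect √2 × Φ⁻¹(0.67) = 0.622 gives 90.05% power at 147. The figure reproduces.

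**2. Endpoints affected (section 10.2.2).** Ten assayed: oestradiol, oestrone, oestrone sulfate, androstenedione, FSH, LH, DHT, progesterone, SHBG, total testosterone. One derived: free testosterone. Plus serum PSA. Total 10 + 1 + 1 = 12.

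**3. How many patients the rule can remove.** 14/147 = 9.5%, so imputation is not triggered. 15/147 = 10.2%, so it is. The most that can be excluded with no route back is 14, and only if every one of them has paired blood.

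**4. Cost in precision.** With losses in proportion to the allocation, the standard-error ratio is √(147/(147 − k)), where k is the number lost. Power is Φ(0.62 × √(0.1875 × (147 − k)) − 1.96), where 0.1875 = 0.75 × 0.25. The 0.62 is the Ki67 design effect, borrowed only to give a scale; the protocol sets no target effect for the serum endpoints.

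| Assumed Ki67 failure | Patients lost | SE increase | Power at 0.62 |
|---|---|---|---|
| None | 0 | 0 | 90.2% |
| 1% | 1.5 | 0.5% | 90.0% |
| 5% | 7.4 | 2.6% | 88.7% |
| 9.5% (ceiling) | 14 | √(147/133) − 1 = 5.1% | 87.2% |

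If all 14 were on enobosarm, the arms would be 36.75 and 110.25 − 14 = 96.25. The ratio is √[(1/36.75 + 1/96.25)/(1/36.75 + 1/110.25)] = 1.018, an increase of 1.8%, with power 89.2%. The same formula with all 14 taken from control (22.75 and 110.25) gives 1.209. Nothing in the protocol suggests that pattern, but it shows that 5.1% assumes a proportional loss.

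**5. Early stoppers.** In Table 2 (section 7.2) the row "Collection of blood – trial sample" is marked under premature discontinuation, while the tissue row is marked only at Visit 2. Section 7.4, on interruption for toxicity, says that both blood and tumour sampling carry on to schedule. The first makes blood without Ki67 plausible in early stoppers; the second points the other way. The protocol does not settle which occurs.

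**The case against.** The strongest reply is that the text is less absolute than it looks. The re-admission clause exists. Table 3 of section 10.5.1 also gives a missing primary endpoint the action "Exclude from per protocol analysis", which would be redundant if nobody in the full analysis set could lack Ki67. That ambiguity is real. It does not remove the problem: the definition itself requires the assessment, re-admission is permissive, the ITT population it refers to is not defined as a separate set, and imputation is not attempted at or below 10% missing.

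A second reply is that tissue will rarely fail. Surgery is arranged as standard care before treatment starts, a single available core goes to the FFPE block (section 7.3.6), and standard-care blocks are also requested (section 8.2). This stands as a reason to expect a small loss. On the other side, the baseline sample is whatever remains of the diagnostic core, section 12.2 makes the research biopsy optional, and section 10.5.5 itself provides for more than 10% missing. The expected loss to follow-up of under 1% in section 10.3 is not a tissue-failure rate.

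A third reply concerns stoppers. A reader might infer that early stoppers are dropped from the serum endpoints. The documents do not support that. Stopping drug does not remove anyone from the full analysis set; only a missing Ki67 does, and partial dosing bears on the per-protocol set alone, after review. Blood taken at premature discontinuation is also not automatically a two-week value, which is what sections 4.3 and 10.2.2 define.

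Finally, it may be said that this belongs in the statistical analysis plan. But the protocol does not leave the sets open; it states them.

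**Conclusion.** The point holds for the secondary endpoints only. As written, both efficacy sets depend on Ki67, so patients with paired blood but no evaluable Ki67 are left out of twelve serum endpoints unless imputation is triggered and re-admits them. Up to 14 of 147 patients could be lost, raising the standard error by about 5.1% under proportional loss, or about 1.8% if all are on enobosarm. This assumes that every tissue failure has complete paired blood. The actual failure rate is unknown.

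A reader might also infer that serum data are lost whenever tissue fails, or quote losses of 22 or 29 patients at 15% or 20% failure. Those rates lie above the trigger, where patients may be re-admitted, so the text does not support them as losses. Selection by arm is possible and potentially matters more than the precision, but it is neither established nor quantifiable from the protocol.

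The size is modest. The change is worth making because the exclusion serves no purpose for these endpoints and costs almost nothing to remove.

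**What to change.** Add to section 10.5.1:

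> Each blood-based secondary efficacy endpoint is analysed by randomised arm in all randomised patients, subject to exclusions a) to c), who have a baseline and a two-week (Visit 2) value of that endpoint, whether or not Ki67 is evaluable. The analysis in the Ki67-evaluable set is a sensitivity analysis.

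The wording keeps the existing exclusions and the two-week timepoint, so it changes the population and not the endpoint. Separately, reconcile Table 2 with section 7.4 on which samples are expected after a patient stops trial drug.

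The cost is one sentence, and denominators that differ between endpoints in the tables. No new data are needed, and the primary analysis, the safety set and N = 147 stay as they are.
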